7.5 Special Adverse Events Handling Principles

7.5.1 Handling Principles for Leukocytosis

Subjects who develop leukocytosis should be graded per NCI CTCAE Version 5.0 and treated by the following measures in a timely manner:

- Hydroxyurea oral therapy is immediately given, and it can be used at up to 2 to 3 g twice a day (see [Table 10](#))
- Leukapheresis is performed if clinically necessary

When the above treatment measures are unable to effectively control the clinical symptoms, HMPL-306 treatment should be suspended. After the clinical symptoms have been fully relieved, the HMPL-306 administration can be resumed. The dose of the drug resumed should be decided after discussion with the Sponsor-appointed medical monitor.

Table 10 Hydroxyurea Initial Dose Reference

Hydroxyurea Dose	Peripheral White Blood Cell Count	Absolute Value of Increase from Baseline of Peripheral White Blood Cell Count
1000 mg QD	$25 \times 10^9/L$ to $50 \times 10^9/L$	$15 \times 10^9/L$ to $<30 \times 10^9/L$
2000 mg BID	$>50 \times 10^9/L$ to $75 \times 10^9/L$	$30 \times 10^9/L$ to $<50 \times 10^9/L$
3000 mg BID	$>75 \times 10^9/L$	$\geq 50 \times 10^9/L$

BID = twice daily; QD = once a day.

8 SAFETY MONITORING

8.1 Definitions

8.1.1 Adverse Event

An AE is any unfavorable and unintended sign, symptom, or disease temporally associated with the use of an investigational medicinal product or other protocol-imposed intervention, whether or not considered related to the medicinal product.

8.1.2 Serious Adverse Event

An AE is considered “serious” if, in the view of either the investigator or the Sponsor, it results in any of the following outcomes:

- Death
- A life-threatening AE. An event is considered “life threatening” if, in the view of the investigator, its occurrence places the subject at immediate risk of death. It does not include an AE or suspected adverse reaction that, had it occurred in a more severe form, might have caused death
- Inpatient hospitalization or prolongation of existing hospitalization
- A persistent or significant incapacity or substantial disruption of the ability to conduct normal life functions
- A congenital anomaly/birth defect
- Important medical events that may not result in death, be life-threatening, or require hospitalization may be considered serious when, based on appropriate medical judgment, they may jeopardize the subject and may require medical or surgical intervention to prevent one of the outcomes listed in this definition. Examples of such medical events include allergic bronchospasm requiring intensive treatment in an emergency room or at home, blood dyscrasias or convulsions that do not result in inpatient hospitalization, or the development of drug dependency or drug abuse
- Signs, symptoms, or the clinical sequelae of a suspected overdose of either study drug or a concomitant medication. Overdose per se will not be reported as an AE/serious adverse event (SAE) unless it is an intentional overdose taken with possible suicidal/self-harming intent. Such overdoses should be reported regardless of sequelae

8.1.3 Dose-Limiting Toxicity

DLT is defined as the occurrence of any of the following TEAEs during the DLT assessment window, unless the TEAEs are clearly unrelated to the study drug or judged by the investigator as not clinically significant.

1. Non-hematologic toxicities:
 - Any Grade 4 non-hematologic toxicity
 - Grade 3 non-hematologic toxicity, except for the following conditions:

- Recovered to Grade ≤ 1 within 3 days after supportive therapy is administered for nausea, vomiting, diarrhea, constipation, fatigue, and electrolyte imbalance
 - Grade 3 hypothyroidism, adrenal gland or pituitary insufficiency, and inflammatory reactions at the tumor site
 - Grade 3 hypertension downgraded to Grade ≤ 1 within 1 week with appropriate supportive therapy
2. Hematologic toxicity:
- Grade ≥ 3 febrile neutropenia (neutrophil count $< 1.0 \times 10^9/L$, accompanied with a single body temperature measurement of $\geq 38.3^\circ C$ or $\geq 38^\circ C$ persisting for 1 hour)
 - Grade 4 neutropenia
 - Grade 4 thrombocytopenia
 - Grade 3 thrombocytopenia accompanied with clinically significant bleeding, in addition to that requiring transfusion
 - Grade 4 anemia requiring a dose delay of ≥ 14 days
3. Any life-threatening complication or abnormality not covered in the NCI CTCAE Version 5.0.

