4.1.1 Part 1 (Dose Escalation)

The first part of the study is dose escalation where cohorts of subjects will receive ascending oral doses of HMPL-306 to determine maximum tolerated dose (MTD) and/or the recommended phase 2 dose (RP2D). The modified toxicity probability interval-2 (mTPI-2) (Yang 2015) design will be utilized for dose escalation until determination of MTD/RP2D. The mTPI-2 method uses a Bayesian framework and a hierarchical model to compute the dose escalation based on the interval between the toxicity rate of each dose level and target probability (Guo 2017). This study is designed targeting a dose-limiting toxicity (DLT) rate of 25% with an equivalence interval of 20% to 30%.

Like the 3+3 design, the mTPI-2 method incorporates pre-specified escalation rules that can be presented in a table (Table 6). As shown in Table 6, the number of subjects dosed at a given dose level is shown in the columns, while the rows indicate the number of DLTs experienced. The escalation/de-escalation rules from the table will be used for each dose level evaluated; the subject numbers and DLTs do not carry over from cohort to cohort. As an example, within a cohort:

- If none of the 3 subjects experience a DLT → escalate the dose (“E” at column 3 row 0) to the next dose level cohort
- If 1 out of 4 subjects experience a DLT → stay at the same dose level (“S” in column 4 row 1)
- If 2 out of 3 subjects experience a DLT → de-escalate to a lower dose level (“D” at column 3 row 2)
- If 3 out of 3 subjects experience a DLT → the dose is determined to be unacceptably toxic and will not be used again, de-escalate to a lower dose level (“DU” at column 3 row 3)

The following rules apply during dose escalation:

- The initial dose will be 100 mg PO, once a day (QD)
- Although in the mTPI-2 method the cohort size is not fixed, at least 3 subjects will be enrolled at each dose level. When all subjects at a dose level complete DLT assessment, the study will escalate to the next dose level and another 3 subjects will be recruited in the order of dose escalation plan until RP2D or MTD Table 6. A minimum of 3 subjects will be enrolled in each cohort.
- The sample size of a dose cohort that has already passed the preliminary DLT assessment (1 to 3 subjects) and has shown efficacy can be extended to 12 cases in order to further evaluate the safety and efficacy signals of this dose
- The study stage will prematurely end when any of the following conditions are met:

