- Excessive toxicity is present in the initial dose
- Although no excessive toxicity is present in the first dose level cohort, if the dose returns to the initial dose according to the rules in Table 6 and excessive toxicity is present at the initial dose (for example, 4 or more DLTs are observed in 6 subjects)

Please see Section CCI.

A cycle of study treatment is defined as 28 days of continuous daily dosing, according to the cohort and dose level. At the starting dose, subjects will be administered HMPL-306 at CCI mg PO, QD, and the dose will escalate successively according to the sequence of CCI mg QD, CCI mg QD, CCI mg QD, CCI mg QD, CCI mg QD, CCI mg QD, and CCI mg QD. (see Table 5). The modified Fibonacci design will be used to escalate the dose (see Table 6 for details on the dose escalation decision).

The addition of dose levels 5 to 8 in Protocol Amendment 2 is based on the cumulative safety and preliminary PK and PD data review conducted by the Sponsor and the Safety Review Committee (SRC) members. Following completion of enrollment of dose levels 1 to 4, the PD data reviewed did not demonstrate the desired level of 2-HG inhibition for the Sponsor and the SRC members to declare the RP2D to move to Part 2. Pharmacokinetic data review showed dose proportional increase in PK exposure over the dose range of CCI mg to CCI mg QD. As there were no DLTs or safety concerns noted in dose levels 1 to 4, the Sponsor and SRC members agreed to continue escalation at higher dose levels.

Table 5 Subject Dose Grouping (Dose Escalation Plan)

Dose Level	Dose of HMPL-306 PO, QD ^a with water
1	CCI mg
2	mg
3	mg
4	mg
5	mg
6	mg
7	mg
8	mg

PO = orally; QD = once a day.

Table 6 mTPI-2 Decision Table for Dose Selection

Target toxicity probability (pT)=25%; $\epsilon_1=0.05$; $\epsilon_2=0.05$

	Number of Patients											
	1	2	3	4	5	6	7	8	9	10	11	12
0	E	E	E	E	E	E	E	E	E	E	E	E
1	D	D	D	S	S	E	E	E	E	E	E	E
2		DU*	D	D	D	D	S	S	S	S	E	E
3			DU	DU	DU	D	D	D	D	D	S	S
4				DU	DU	DU	DU	DU	D	D	D	D
5					DU	DU	DU	DU	DU	DU	D	D
6						DU	DU	DU	DU	DU	DU	DU
7							DU	DU	DU	DU	DU	DU
8								DU	DU	DU	DU	DU
9									DU	DU	DU	DU
10										DU	DU	DU
11											DU	DU
12												DU

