8.5 Assessment of Severity

Investigators will seek information on AEs and SAEs at each subject contact. All AEs and SAEs, whether reported by the subject or noted by authorized study personnel, will be recorded in the subject's medical record and on the appropriate AE/SAE form.

For each AE and SAE recorded on the applicable eCRF, the investigator will make an assessment of severity through clinical description by referring to the 5-grade determination standard in the NCI CTCAE Version 5.0. Please use the guideline below for the assessment of severity when the observed or reported AE is not listed in the NCI CTCAE Version 5.0:

- Grade 1: Mild; asymptomatic or mild symptoms; clinical or diagnostic observations only; intervention not indicated
- Grade 2: Moderate; minimal, local, or noninvasive intervention indicated; limiting age-appropriate instrumental activities of daily living (ADLs). (Note: Instrumental ADLs

refer to preparing meals, shopping for groceries or clothes, using the telephone, managing money, etc.)

- Grade 3: Severe or medically significant but not immediately life threatening; hospitalization or prolongation of hospitalization indicated; disabling; limiting self-care ADLs (Note: Self-care ADLs refer to bathing, dressing and undressing, feeding self, using the toilet, taking medications, and not bedridden).
- Grade 4: Life-threatening consequences; urgent intervention indicated
- Grade 5: Death related to AE

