9.1.1 Statistical Hypothesis

No formal hypothesis testing is planned for this study. For efficacy endpoints, the study will provide the estimates and the associated 95% CI for precision.

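### The investigator alone can exempt any listed event from the DLT count, with no recorded reason or SRC ruling required before Table 6 is applied

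*Protocol*

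**What the plan says.** Protocol 8.1.3 lists the toxicities that count as DLTs: non-hematologic, hematologic, and life-threatening events outside CTCAE. It sets out specific Grade 3 exceptions, some with recovery times. The sentence introducing the whole list qualifies it: an event counts "unless the TEAEs are clearly unrelated to the study drug or judged by the investigator as not clinically significant". Section 4.1.1 repeats the qualification. Neither section defines clinical significance for this purpose, limits it by grade, or asks for a reason or a second opinion.

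The count feeds the mTPI-2 rule in Table 6, which targets 25% with an equivalence interval of 20% to 30%. The first worked example is "If none of the 3 subjects experience a DLT → escalate the dose". On cohort size, "at least 3 subjects will be enrolled at each dose level", and a dose that passes its preliminary assessment and shows efficacy "can be extended to 12 cases".

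Section 8.2.3 asks for confirmation to the sponsor within 2 business days, but only for DLT events. Under 4.1.1 the SRC, made up of the sponsor and investigators, decides on escalation, and under 11.1.1 it reviews all safety data. No independent monitoring is planned (11.1). SAP 5.2.11.1 summarizes DLTs by patient, SOC, PT and highest grade. It has no count of listed events that were exempted.

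**The concern.** The escalation decision starts from two numbers: subjects treated and subjects with a DLT. The second passes through a filter applied by an investigator who knows the dose, and the filter works in one direction. It can take a listed event out of the count but cannot put one in. The join between the two grounds is an *or*, so an event that is plausibly drug-related can be removed on significance alone. This includes Grade 4 non-hematologic toxicity, Grade 4 neutropenia and the life-threatening events in the third item.

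At stake are the input to Table 6 and a primary endpoint. If exemptions occur, the 25% target applies to listed events net of an unrecorded judgement, and nobody reading the SAP's DLT table can tell how large that judgement was.

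**Working it through.** **1. The plan's own table.** Inputs from 4.1.1: target 0.25 and ε1 = ε2 = 0.05, giving 0.20 to 0.30. Assumed, because the protocol does not state them: a Beta(1,1) prior, sub-intervals 0.10 wide on either side of the equivalence interval, and DU when the decision is D and P(p > 0.25 | data) > 0.95. For n = 1 to 12 there are 78 + 12 = 90 cells, and all 90 agree with Table 6. For example, 2/3 gives P(p > 0.25) = 0.9492, hence D; 3/4 gives 0.9844, hence DU. The table is sound, so the question concerns only the count put into it.

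**2. One event removed, read from Table 6.**

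| Listed-event count | Decision | After one exemption | Decision |
|---|---|---|---|
| 1/3 | D | 0/3 | E |
| 2/6 | D | 1/6 | E |
| 4/12 | D | 3/12 | S |
| 3/12 | S | 2/12 | E |

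Down any column the order is E, S, D, DU. At fixed n, an exemption therefore leaves the decision unchanged or makes it less conservative.

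**3. Evaluability.** A subject is DLT-evaluable after receiving at least 75% of the assigned dose in the window (0.75 × 28 = 21 daily doses), or if a DLT prevented completion (4.1.1, 9.1.3). Section 7.4.1 allows suspension for Grade 3 and 4 events that are not DLTs. A subject whose event is exempted and who then takes 20 or fewer full doses (20/28 = 71%) meets neither route and is replaced (6.2.1.3). That event leaves both numerator and denominator.

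**4. Illustration of size.** Let p be the true share of subjects with a listed, not clearly unrelated event, and w the share of those subjects whose event is exempted. The documents give no value for w, so a range is shown. The counted rate is q = p(1 − w), and P(0/3) = (1 − q)³.

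| w | q at p = 0.40 | P(0/3) | q at p = 0.50 | P(0/3) |
|---|---|---|---|---|
| 0 | 0.40 | 21.6% | 0.50 | 12.5% |
| 0.10 | 0.36 | 26.2% | 0.45 | 16.6% |
| 0.25 | 0.30 | 34.3% | 0.375 | 24.4% |
| 0.50 | 0.20 | 51.2% | 0.25 | 42.2% |

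At n = 6 Table 6 escalates on 0 or 1 DLT. With p = 0.40 the probability is 23.3%, 30.1%, 42.0% and 65.5% for the same four values of w.

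The share that brings a dose down to a counted 30%, the top of the equivalence interval, is 1 − 0.30/p: 25% at p = 0.40 and 40% at p = 0.50.

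**5. Sensitivity of step 4.** The formula takes w per subject. If instead each affected subject has two listed events, each exempted independently with probability 0.50, the subject drops out of the count only when both are exempted: q = 0.40 × (1 − 0.50²) = 0.30, and P(0/3) = 34.3% rather than 51.2%. Several events per subject weaken the effect.

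**The case against.** The strongest reply is that Table 6 is not the whole decision. The SRC determines whether it is safe to go on and reviews all safety data. AEs are collected regardless of attribution (8.2.1). Either the investigator or the sponsor can class an event as serious (8.1.2), and SAEs reach the sponsor within 24 hours (8.2.2), faster than the DLT route. An exempted life-threatening event would hardly go unseen. SAP 5.2.11.2 also lists grade, relationship and DLT flag for each AE. All of this stands, and it limits the consequence. It does not close the gap: no text asks the SRC to rule on an exemption or to restore an event to the count before Table 6 is read.

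The exemption may also be intended for trivial laboratory findings, and the 25% target refers to DLTs as defined, clinical significance included. Some exemptions could thus be correct. Without a recorded reason, however, correct ones cannot be told from incorrect ones.

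Three stronger readings are tempting, and the documents do not support them:

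- A reader might set the clause against the severity scale in 8.5, "Grade 4: Life-threatening consequences; urgent intervention indicated", and call it a contradiction. That scale applies only to AEs not listed in CTCAE v5.0.
- A reader might call the Grade 3 exceptions in 8.1.3 redundant. They apply without any judgement of significance and cover events that may well be significant, so the two provisions exempt different sets.
- A reader might infer that the absence of DLTs at dose levels 1 to 4 came from exemptions. Section 4.1.1 reports no DLTs or safety concerns after a cumulative review, and nothing shows that any event was exempted.

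**Conclusion.** The point holds as one of unadjudicated filtering. A listed, possibly drug-related event of any grade can leave the DLT count on the investigator's judgement alone, the effect on Table 6 runs in one direction, and a single exemption is enough to turn D into E at 1/3 or 2/6. Those statements rest on the text and on Table 6, with no assumption about frequency.

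The probabilities do rest on assumptions: an exemption share the documents do not give, one listed event per affected subject, and escalation following Table 6 without SRC intervention. It would go too far to conclude that a dose at 40% is more likely than not to pass. The 51% needs half of the affected subjects to be exempted, and it falls when subjects have several listed events or the SRC holds the dose.

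The protocol supplied is Amendment 2, while the SAP is based on Amendment 3. SAP Section 7 mentions a protocol-defined DLT-equivalent summary that does not appear in the readable Amendment 2 text, so the DLT wording may have changed and the clause should be checked there.

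**What to change.** This review does not propose which events should be DLTs; changing that has dosing consequences under 7.4.1. The sponsor should reconcile the open-ended exemption with the specific criteria and exceptions in 8.1.3, after checking Amendment 3.

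- **Protocol 8.2.3 and 4.1.1.** Require every event in the window that meets a listed criterion and is not clearly unrelated to be reported, with any proposed exemption and its reason. The SRC decides and documents the outcome before Table 6 is applied.
- **SAP 5.2.11.1.** Tabulate and list DLTs with and without exempted events, deriving candidates from the Cycle 1 grade, relatedness and DLT-flag data already collected. The listing should include exempted subjects who were replaced as not evaluable.

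The SAP reports that Part 2 did not open and covers Part 1 only. If escalation is already complete, the reporting step cannot work prospectively, but the SRC can make the same review before database lock and the SAP step keeps its full value.

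The cost is a little more SRC work, one added table row and one listing.

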2.3 Benefit/Risk Assessment

2.3.1 Risk Assessment

HMPL-306 is in the early stage of development, and the clinical safety profile has not yet been established, but some potential risks have been observed from nonclinical studies and clinical data from drugs in the same class. Measures for managing these potential risks are as shown in [Table 3](#).

Table 3 Summary of Potential Risks of HMPL-306

Potential Risk of Clinical Significance	Summary of Data/Rationale for Risk	Mitigation Strategy
Gastrointestinal disorders	[REDACTED] was observed in rats with doses up to [REDACTED] mg/kg of HMPL-306. Gastrointestinal diseases such as nausea, vomiting, diarrhea, mucositis, constipation, abdominal pain, etc. occurred in clinical studies of both enasidenib and ivosidenib.	General guidance to be provided in the protocol for dose interruption/reduction/discontinuation in response to AEs.
Embryotoxicity	At the present stage, the study of effect of HMPL-306 on embryo development has not been implemented. Enasidenib and ivosidenib were associated with maternal toxicity and adverse embryo-fetal effects in pregnant rats.	Women who are pregnant (pregnancy test is positive before drug administration) or breastfeeding will be excluded from the study. Male with partners of childbearing potential or female subjects of childbearing potential will be required to use effective contraception

Table 3 Summary of Potential Risks of HMPL-306

Potential Risk of Clinical Significance	Summary of Data/Rationale for Risk	Mitigation Strategy
		methods. Female subjects of childbearing potential will be tested for pregnancy at every cycle.
Non-infectious leukocytosis	Neutrophil count was seen increased by CCI% in animals administered HMPL-306 (CC mg/kg/day), and no abnormalities were observed at the end of the recovery period. Non-infectious leukocytosis occurred in clinical trials of both enasidenib and ivosidenib.	Peripheral white blood cell count will be monitored at baseline and during the study at regular intervals, particularly at least once weekly in the first 2 cycles (28 days/cycle) of the initial drug administration. Afterward, it will be monitored once a cycle.

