6.1.10.1 Hematology

Hematology, including red blood cell count, hemoglobin, hematocrit, white blood cell count with differential and classifications (neutrophils [ANC and neutrophils %], lymphocytes [absolute lymphocyte count and lymphocytes %], eosinophils [absolute eosinophil count and eosinophils %], monocytes [absolute monocyte count and monocytes %], and basophils [absolute basophil count and basophils %]), and platelet count, will be performed during the study according to the schedule in [Table 1](#) and [Table 2](#). If abnormal or primitive immature cells are seen, they will also be recorded. Any additional routine blood tests during the study shall be arranged by the investigator as needed.

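### The DLT definition has no entry that reaches leukocytosis, so a life-threatening, drug-related case adds nothing to the mTPI-2 count unless a separate non-hematologic complication is recorded

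*Protocol*

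**What the plan says.** Protocol 8.1.3 is an enumerated definition: "DLT is defined as the occurrence of any of the following TEAEs during the DLT assessment window". It has three items.

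- Item 1 (non-hematologic) includes "Any Grade 4 non-hematologic toxicity", and Grade 3 events with listed exceptions.
- Item 2 (hematologic) lists Grade 3 or higher febrile neutropenia, Grade 4 neutropenia, Grade 4 thrombocytopenia, Grade 3 thrombocytopenia with significant bleeding, and "Grade 4 anemia requiring a dose delay of" at least 14 days. It has no general Grade 4 entry.
- Item 3 is the catch-all: "Any life-threatening complication or abnormality not covered in the NCI CTCAE Version 5.0".

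On leukocytosis, Table 3 (Protocol 2.3.1) names the non-infectious form as a potential risk of HMPL-306, citing animal data and the drug class: "Non-infectious leukocytosis occurred in clinical trials of both enasidenib and ivosidenib". Section 7.5.1 directs: "Subjects who develop leukocytosis should be graded per NCI CTCAE Version 5.0 and treated by the following measures in a timely manner". The measures include hydroxyurea and "Leukapheresis is performed if clinically necessary", with suspension of study drug if symptoms are not controlled.

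Section 4.1.1 feeds the DLT count at each dose level into Table 6. It defines a DLT-evaluable subject as one who received at least 75% of the assigned dose in the 28-day window, or who did not complete the window because of a DLT. Other subjects are replaced.

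**The concern.** In an mTPI-2 design the DLT count is the only toxicity input to the decision table, and DLTs and the MTD/RP2D are primary endpoints. An event that the protocol expects as a class risk, and for which it plans leukapheresis and interruption, should have a defined place in that count when it is life-threatening and drug-related. Here it has none. The rule would read such a cohort as less toxic than it was, and the DLT rate reported under SAP 5.2.11.1 would leave the event out. The same applies to any other Grade 4 hematologic event that CTCAE grades and item 2 does not list.

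The qualifier at the head of 8.1.3 (clearly unrelated, or not clinically significant in the investigator's judgement) does not help. It can remove a listed event but cannot add an unlisted one.

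**Working it through.** **Step 1: test leukocytosis against each item of 8.1.3.**

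- Item 1 needs a non-hematologic event. The protocol does not define hematologic, but Section 6.1.10.1 places "white blood cell count with differential and classifications" under hematology, so the natural reading excludes leukocytosis. A reader who classed it as non-hematologic would count Grade 4.
- Item 2 does not list it.
- Item 3 needs an event outside CTCAE v5.0. Section 7.5.1 has leukocytosis graded by CTCAE v5.0, so item 3 is closed.

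Nothing in the available protocol or in the SAP adds it.

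**Step 2: what happens to the subject.** 75% of 28 daily doses is 0.75 × 28 = 21.

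- At least 21 doses taken: evaluable, no DLT.
- Fewer than 21: the second limb of the evaluability rule needs a DLT, so the subject is non-evaluable and replaced. The event leaves both numerator and denominator.

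Either way the event adds no DLT.

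**Step 3: reproduce Table 6.** Inputs from 4.1.1 and Table 6: target 25%, ε1 = ε2 = 0.05. Assumed, because the documents do not state them: a Beta(1,1) prior, intervals of width 0.1, and DU when P(p > 0.25 | data) > 0.95. The posterior is Beta(1+x, 1+n−x), and the decision follows the interval with the largest probability per unit width. All 90 cells of Table 6 are reproduced. For example:

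- 0/3: Beta(1,4), CDF 1 − (1−p)^4. Mass on 0–0.1 is 0.344, on 0.1–0.2 is 0.247, on 0.2–0.3 is 0.170. The largest lies below the equivalence interval: E.
- 1/3: Beta(2,3), CDF 1 − (1−p)^4 − 4p(1−p)^3. Mass on 0.2–0.3 is 0.168, on 0.3–0.4 is 0.177, on 0.4–0.5 is 0.163. The largest lies above the interval: D. P(p > 0.25) = 0.738, below 0.95, so not DU.

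**Step 4: effect of counting the event, read from Table 6.**

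| Evaluable n | Other DLTs | Such events | As written | If counted |
|---|---|---|---|---|
| 3 | 0 | 1 | E | D |
| 4 or 5 | 0 | 1 | E | S |
| 6 | 0 | 1 | E | E |
| 6 | 0 | 2 | E | D |
| 4 | 1 | 1 | S | D |
| 6 | 1 | 1 | E | D |
| 7 or 9 | 1 | 1 | E | S |

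Across all positions with x < n and n = 1 to 12, one more DLT changes the decision in 31 of 78. These positions are not equally likely, so this is not a probability.

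**Step 5: illustration with assumed rates.** The documents give no rate for life-threatening leukocytosis. Let p be the rate of listed DLTs and q the rate of the unlisted event, independent, with the subject remaining evaluable. The total rate is 1 − (1−p)(1−q). At n = 3, E requires 0 DLTs, so P(E) = (1 − rate)^3.

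With p = 10%, P(E) as written is 0.9^3 = 73% for every q:

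| q | Total rate | P(E) at n = 3 if counted |
|---|---|---|
| 5% | 14.5% | 0.855^3 = 63% |
| 10% | 19% | 0.81^3 = 53% |
| 20% | 28% | 0.72^3 = 37% |

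If the listed rate sits at the 25% target, the total is 0.25 + 0.75q. It passes the 30% upper bound once q exceeds 0.05/0.75 = 6.7%.

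**The case against.** The case on the other side has several parts.

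- **Complications can count.** Section 8.7.2 exempts severe or serious secondary events from being folded into their cause. A Grade 4 organ complication, or a Grade 3 one outside the exceptions, recorded separately is a DLT under item 1. This stands and narrows the gap to the leukocytosis itself.
- **The SRC decides formally.** Sections 4.1.1 and 11.1.1 give it the safety data and the escalation decision. The event would also be an SAE reported within 24 hours, and would appear in the TEAE summaries and the adverse event listing. This stands as mitigation. It does not change the Table 6 count or the DLT summary.
- **Leukocytosis is not unique in having its own guidance.** QT prolongation has Section 7.4.3 and Table 9. This is correct, but a Grade 4 QT event falls under item 1 as non-hematologic.
- **The omission may be deliberate.** Amendment 1 revised the DLT list at FDA request and did not add leukocytosis. That is possible, but the documents give no reason for leaving it out.
- **The text may have changed.** The SAP follows Amendment 3, and the protocol available is Amendment 2. SAP Section 7 drops a DLT-equivalent summary, a term absent from the available protocol, because those events were not well collected. Amendment 3 may differ, but that summary will not fill the gap.

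A reader might infer more: that every such subject is entered as evaluable without a DLT, that one event always reverses the decision, or that escalation has gone ahead wrongly. The documents support none of these. Below 75% of dose the subject is replaced. The reversal from E to D with one event and no other DLT holds at n = 3 but not at 4 to 6. Section 4.1.1 reports no DLTs or safety concerns at dose levels 1 to 4.

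**Conclusion.** The gap holds on the text. Read as written, 8.1.3 gives a life-threatening, drug-related leukocytosis no route into the DLT count unless a separate Grade 3 or 4 non-hematologic complication is recorded. With no other DLT, counting one event would move Table 6 from E to D at n = 3 and from E to S at n = 4 or 5, and would leave n = 6 unchanged.

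The conclusion rests on reading leukocytosis as hematologic and on Amendment 2. The Table 6 shifts do not depend on any assumed rate. The escalation probabilities do, and they also assume that the table is followed mechanically, which the SRC need not do. The weakness is in the definition of a primary endpoint, and there is no evidence that it altered a dose decision.

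**What to change.** The sponsor and SRC should reconcile Table 3 with Sections 7.4.1, 7.5.1 and 8.1.3, and state four things:

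1. That item 3 of 8.1.3 no longer excludes a life-threatening event merely because CTCAE grades it.
2. How life-threatening hematologic events outside item 2 enter the mTPI-2 count.
3. That the existing anemia, neutropenia and thrombocytopenia rules still govern those events. Without this, a catch-all for anything not otherwise listed could pull in Grade 4 anemia without the 14-day delay that item 2 requires.
4. Whether 7.4.1 or 7.5.1 governs dosing when such an event occurs in the DLT window. Under 7.4.1 a DLT leads to suspension, then resumption at the previous lower dose or termination, and a subject without a DLT may not be reduced. Section 7.5.1 treats first, suspends if symptoms are not controlled, and leaves the resumed dose to discussion with the medical monitor. The two already sit awkwardly together, and a DLT label would sharpen the conflict.

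The qualifying grade and the management rule are for the sponsor and SRC to set. Amendment 3 should be checked first in case it already does this.

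The cost is a text change in linked sections. No extra sampling is needed, because Table 1 already schedules hematology on Days 8, 15 and 22 of Cycle 1. The small downside is that a rare event could count toward de-escalation.
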